9.3 Analysis of Laboratory Data

Data collected from central and local laboratories, including additional laboratory testing due to an SAE, will be used in all analyses. Change from baseline will be summarized and presented for key lab parameters at scheduled post-baseline visits. Baseline is defined as the last non-missing observation before the first dose of study drug or randomization if no study drug is given.

For shifts relative to National Cancer Institute Common Toxicity Criteria for Adverse Events, baseline and post-baseline laboratory observations will be categorized as Grade 0, Grade 1, Grade 2, Grade 3, or Grade 4 according to NCI CTCAE grading. The baseline grade is defined as the grade of the last measurement collected on or prior to the first dose of study drug (or randomization for non-treated subjects). In cases where multiple values are collected on the same day, the maximum grade value will be selected as the value for that day for post-baseline values and the minimum grade will be selected as the value for that day for baseline values. If a subject had missing baseline and non-missing post-baseline for a given lab, the baseline grade will be assumed to be Grade 0. The maximum NCI toxicity grade value is the value with highest NCI toxicity grade collected after the first dose of study drug.

For each variable, cross tabulation tables will be generated that cross tabulate the number of subjects with baseline values of Grade 0, Grade 1, Grade 2, Grade 3, or Grade 4 versus maximum post-baseline values of Grade 0, Grade 1, Grade 2, Grade 3, or Grade 4. Subjects with missing measurements will be counted in the "missing" category. All treated subjects will be included in the cross tabulation regardless of whether baseline or post-baseline measurements are collected.

The laboratory shifts tables based on the two criteria below will be generated for each laboratory tests related to CTCAE:

1. Shifts from Grade 0 (Normal) at baseline to Grade 1 - 4 post-baseline (maximum) and worsening from an abnormal baseline value of at least one grade up post-baseline (maximum).
2. Shifts from Grade 0 - 2 at baseline to Grade 3 or 4 post-baseline (maximum) and from Grade 3 at baseline value to Grade 4 post-baseline (maximum).

The shift table analyses will include post-baseline measurements within 30 days of the last dose of the study drug. Detailed listings of all data for subjects experiencing NCI CTCAE Grade 3 to 4 blood chemistry and hematology values will be provided.

For key lab parameters including platelet count, lymphocytes, neutrophils, hemoglobin, total bilirubin, ALT, AST, and alkaline phosphatase, boxplots of laboratory values and summary tables will be displayed at scheduled visits.

Assessment of Hepatotoxicity

Elevations relative to the upper limit of normal (ULN) in ALT, AST, total bilirubin, and alkaline phosphatase as outlined in the US FDA Guidance for Industry⁸ pertaining to premarketing clinical evaluations for drug-induced liver injury (DILI) will be summarized using the maximum post-baseline values. Laboratory values collected no more than 30 days following the last date of study drug will be used in the analysis.

The number and percentage of subjects who have at least one observed post baseline value meeting the following criteria will be tabulated by treatment:

- ALT: $> 3 \times$, $> 5 \times$, $> 10 \times$, or $> 20 \times$ ULN
- AST: $> 3 \times$, $> 5 \times$, $> 10 \times$, or $> 20 \times$ ULN
- Total bilirubin: $> 1.5 \times$, $> 2 \times$ ULN
- Alkaline phosphatase: $> 1.5 \times$ ULN
- ALT and/or AST $> 3 \times$ ULN and total bilirubin $> 1.5 \times$ ULN at any visit
- ALT and/or AST $> 3 \times$ ULN and total bilirubin $> 2 \times$ ULN at any visit
- ALT and/or AST $> 3 \times$ ULN and total bilirubin $> 2 \times$ ULN within 72 hours
- ALT and/or AST $> 3 \times$ ULN and total bilirubin $> 2 \times$ ULN at the same visit

An evaluation of Drug Induced Serious Hepatotoxicity (eDISH) plot of the maximum post-baseline ALT value (as a multiple of ULN) vs. the maximum post-baseline total bilirubin value (as a multiple of ULN), not necessarily concurrent, will be presented, with reference lines for $3 \times$ ULN for ALT and $2 \times$ ULN for total bilirubin. A similar eDISH plot will be presented for AST vs. total bilirubin.

A listing of liver function tests for subjects with observed ALT and/or AST ($> 3 \times$ ULN) accompanied by total bilirubin ($> 2 \times$ ULN) at any time on study will be provided.

9.4 Analysis of Vital Signs

Change from baseline will be summarized and presented for each scheduled post-baseline visit for the vital sign parameters. Baseline is defined as the last non-missing observation before the first administration of study drug or randomization if no study drug is given.

9.5 Safety Subgroup Analyses

The incidence of treatment-emergent AEs overview, treatment-emergent AEs by SOC and PT, and safety topics of interest overview will be assessed for the subgroups defined below:

- Age (18 - < 65 years, ≥ 65 years, ≥ 75 years)
- Gender (Male, Female)
- Race (White, Black or African American, Asian, Other)
- Region (US, Europe, Japan, Other Regions)
- DIPSS+ Risk Group (Intermediate-1, Intermediate-2, High)
- Baseline Platelet Count ($\leq 200 \times 10^9/L$, $> 200 \times 10^9/L$)
- Baseline Renal Function (Normal, Mild Impairment, Moderate Impairment, Severe Impairment)
- Baseline Hepatic Function (Normal, Mild Impairment, Moderate Impairment, Severe Impairment)
- Ethnicity (Hispanic or Latino, Not Hispanic or Latino)

10.0 Other Analyses

Summary statistics of plasma concentration of navitoclax will be tabulated for each visit.

11.0 Interim Analyses

There is no planned interim analysis for efficacy. An independent data monitoring committee will review the unblinded safety data on a regular basis to protect the safety of the subjects enrolled in the study.

11.1 Data Monitoring Committee

An independent data monitoring committee (IDMC) will regularly review unblinded safety data from the ongoing study according to the schedule provided in the IDMC charter, including adverse events and laboratory results. The unblinded safety analyses will be performed by an independent statistical data analysis center (SDAC) external to AbbVie and reviewed by the IDMC. AbbVie personnel will remain blinded and will not have access to the unblinded analyses prepared for the IDMC. The IDMC will provide recommendations to AbbVie as per the IDMC charter.

A separate IDMC charter describes the roles and responsibilities of the DMC members, frequency of data reviews, relevant data to be assessed, and general operations.

12.0 Overall Type-I Error Control

The fixed sequence testing procedure will be performed with a significance level of 0.05 (two-sided) for the primary efficacy endpoint and key secondary efficacy endpoints sequentially. The ranking of the endpoints is described in [Table 1](#). If the statistical test is not significant for the primary efficacy endpoint, then statistical significance will not to be declared for any of the key secondary endpoints.

Except for overall survival and leukemia-free survival, the statistical test of other ranked efficacy endpoints will be performed one-time at the primary analysis of SVR_{35W24} rate or at Week 48, based on the testing sequence in [Table 1](#). The planned alpha spending for overall survival and leukemia-free survival will be based on Lan-Demets alpha spending function with O'Brien-Fleming boundaries and is described in [Table 1](#). The actual stopping boundaries will be derived based on the observed number of events in the extracted database. After the primary analysis of SVR_{35W24}, descriptive OS analyses in addition to the pre-planned analyses at 70% OS and 100% OS may be performed to support regulatory submissions as necessary.

Since there are no efficacy analyses for early stopping planned for the IDMC review, no alpha spending is needed for the IDMC review.

Table 1. Testing Sequence and Alpha Spending (Two-Sided) for Primary and Key Secondary Endpoints

Testing Sequence	Endpoint	Timing of Analysis			
		SVR _{35W24}	Week 48 ^a	70% OS (■ Death Events)	100% OS (■ Death Events)
1	SVR _{35W24} rate	0.05	No Test	No Test	No Test
2	Change from baseline in TSS score at Week 24	0.05	No Test	No Test	No Test
3	SVR ₃₅ rate	0.05	No Test	No Test	No Test
4	Anemia Response	0.05	No Test	No Test	No Test
5	Reduction in grade of bone marrow fibrosis	No Test	0.05	No Test	No Test
6	Overall survival	No Test	No Test	0.0149	0.0455
7	Leukemia-free survival	No Test	No Test	0.0149 ^b	0.0455 ^{b, d}
8	Change in fatigue at Week 24 from baseline	0.05 ^c	No Test	No Test	No Test
9	Change in physical functioning at Week 24 from baseline	0.05 ^c	No Test	No Test	No Test

- a. "Week 48" denotes when the last subject enrolled has been followed up for at least 48 weeks.
- b. Information fraction of OS is used as reference for the planned alpha spending.
- c. Statistical significance will not be claimed until all endpoints ranked above are tested and claimed statistical significance.
- d. The actual stopping boundary will be recalibrated based on the actual number of observed LFS events.

13.0 Version History

Table 2. SAP Version History Summary

Version	Date	Summary
1.0	19 Nov 2020	Original version
2.0	21 June 2021	
The following updates were made:
 
 1. Clarified the handling of missing baseline in the analysis of efficacy endpoints. 2. Clarified the additional analyses to be performed for the primary efficacy endpoint. 3. Clarified the handling of baseline score of 0 in the analysis of total symptom scores. 4. Added erythropoietin supplements to the definition of anemia response. 5. Updated the ranking of the key secondary endpoints based on Protocol Amendment 4. 6. Added the summary of difference and 95% confidence interval for difference to the analysis of response rates. 7. Updated OS projection at the analysis of SVR_{35W24}. 8. Clarified analyses of safety topics of interest and safety subgroups. 9. Corrected typos throughout the document.

Version	Date	Summary
3.0 DRAFT	20 October 2021	
The following updates were made:
 
 1. Clarified the analysis window for SVR_{35W24}. 2. Clarified that subjects with unevaluable spleen volume at baseline will be considered non-responders in the analyses of SVR_{35W24} and SVR₃₅. 3. Clarified that additional descriptive summaries will be provided in the analyses of TSS scores and SVR₃₅. 4. Clarified the analysis window and criteria for anemia response. 5. Clarified that data after disease progression will not be included in the analyses of certain efficacy endpoints. 6. Clarified definition of duration of SVR₃₅. 7. Clarified that the statistical test for change in fatigue from baseline at Week 24 will be based on the data cutoff at the primary analysis of SVR_{35W24}. 8. Added alcohol use to baseline characteristics summary. 9. Clarified that the risk difference and 95% CI for overall incidence for each safety topic of interest will be provided in summary tables in addition to forest plots. 10. Clarified that summary tables will be provided for key laboratory parameters in addition to boxplots. 11. Clarified wording for safety topics of interest. 12. Other editorial edits throughout the document.

Version	Date	Summary
3.0 DRAFT	22 July 2022	
The following updates were made based on [REDACTED]:
 
 1. Updated the handling of subjects without baseline TSS score or with a baseline TSS score of 0 that those subjects will be treated as non-responders in the analysis of TSS_{50W24}. 2. Updated the main analysis method of change from baseline in PROMIS Fatigue at Week 24. 3. Removed overall response of clinical improvement from the ranked key secondary endpoints. 
The following additional updates were made:
 
 1. Updated the ranking of the key secondary endpoints. 2. Updated the analysis convention that stratification factors collected in EDC will be used in the stratified analyses. 3. Updated the categorization of DIPSS+ risk group. 4. Added sensitivity analysis of SVR_{35W24}. 5. Updated the analysis window for TSS_{50W24}. 6. Added sensitivity analysis of TSS_{50W24}. 7. Added analysis of TSS₅₀ at any time, time to first TSS₅₀, time to first SVR₃₅, time to first reduction in grade of bone marrow fibrosis. 8. Updated the analysis for post-baseline RBC transfusion. 9. Clarified the analysis of LFS, PFS and allelic mutations. 10. Added age subgroup to the efficacy subgroup analysis. 11. Added additional variables to baseline characteristics. 12. Other editorial edits throughout the documents.

Version	Date	Summary
3.0 DRAFT	29 November 2022	
The following updates were made [REDACTED]
 
 1. Changed the TSS endpoint from TSS_{50W24} to change in TSS score from baseline at Week 24. 2. Defined main and sensitivity analyses for change in TSS score from baseline at Week 24. 3. Defined TSS_{50W24} as a supplementary analysis. 4. Defined TSS₅₀ rate at any time, time to TSS₅₀, duration of TSS₅₀, TSS response rate based on MCT, time to TSS response, and duration of TSS response as supplementary analyses. 5. Defined TSS Analysis Population. 6. Changed the main analysis of PROMIS Fatigue to linear mixed effects model and defined sensitivity analysis. 
The following additional updates were made:
 
 1. Removed RBC Transfusion at Baseline from the baseline characteristics. 2. Added graphical summary of SVR. 3. Added Grade 3 TEAE and Grade 4 TEAE to AE overview. 4. Other editorial edits.

Version	Date	Summary
3.0	01 April 2023	
The following updates were made [REDACTED]
 
 1. Changed the key secondary endpoint TSS_{50W24} to change in TSS score at Week 24 from baseline. 2. Changed the key secondary endpoint time to deterioration in physical functioning to change in physical functioning score at Week 24 from baseline. 3. Added tipping point analysis for major SVR_{35W24} and TSS_{50W24}. 4. Changed the sensitivity analysis for continuous PRO endpoints to tipping point analysis. 5. Changed the analysis population for TSS analyses to ITT population. The TSS analysis population will be used for sensitivity analysis. 6. Added analysis of change in TSS score from baseline at Week 24 by excluding the fatigue symptom. 7. Clarified that all 7 questions need to be answered to calculate the daily TSS score. 8. Clarified that T-score will be used in the analysis of PROMIS Fatigue total score and raw score will be used in the analysis of PROMIS Fatigue subitems. 
The following additional updates were made:
 
 1. Updated the ranking and analysis timing of the key secondary endpoints. 2. Clarified the strata-adjusted difference between the treatment arms will be summarized for binary endpoints. 3. Added the definition of confirmed disease progression. 4. Added summary of SVR₃₅ rate at Week 12. 5. Added analysis of TSS response based on MCT at Week 24. 6. Added summary of maximum reduction in TSS from baseline at any time. 7. Added the value of MCT for TSS analysis. 8. Updated the definitions of duration of TSS₅₀ and duration of TSS response based on MCT. 9. Clarified that all questions need to be answered to calculate PROMIS Fatigue total score and the subdomain score. 10. Added summary of reduction in grade of bone marrow fibrosis at Week 24

Version	Date	Summary
		
 11. Clarified that additional descriptive OS analysis may be performed based on regulatory interactions. 12. Added summaries for number and amount of PRBC transfusions. 13. Added summaries of $\geq 20\%$ and $\geq 50\%$ reduction in driver gene allele frequency. 14. Updated the summaries of JAK2, CALR, and MPL mutations. 15. Updated the analysis of correlation among efficacy endpoints. 16. Removed "Skin Cancer or Second Malignancies" from the safety topic of interest. 17. Added Ethnicity to safety subgroup analyses. 18. Added Race and Ethnicity to efficacy subgroup analyses. 19. Other editorial edits.

Appendix A. Protocol Deviations

The number and percentage of subjects who reported at least one of the following protocol deviation categories will be provided.

- Subject entered into the study even though s/he did not satisfy entry criteria.
- Subject developed withdrawal criteria during the study and was not withdrawn.
- Subject received wrong treatment or incorrect dose of study.
- Subject took prohibited concomitant medication.

Appendix B. Definition of Safety Topics of interest

Safety topics of interest will be identified using the following search criteria:

Safety Topics of Interest	Criteria for Identification of Events
Thrombocytopenia	PTs: 10043554 Thrombocytopenia 10035528 Platelet Count Decreased
Neutropenia	PTs: 10016288 Febrile Neutropenia 10029354 Neutropenia 10029366 Neutrophil Count Decreased
Hemorrhagic Events	SMQ: 20000038 Haemorrhages (Narrow)
Serious Hemorrhagic Events Concurrent ^a with Grade 3 or 4 Thrombocytopenia	SAEs in the Hemorrhagic Events search concurrent with Grade 3 or 4 AE in Thrombocytopenia search
Serious Infections	SAEs in the SOC of Infections and Infestations
Serious Infections with Concurrent ^a with Grade 3 or 4 Neutropenia	SAEs in the Serious Infections search concurrent with Grade 3 or 4 AE in Neutropenia search
Drug-Induced Liver Injury (DILI) ^b	SMQs: 20000006 Drug Related Hepatic Disorders - Comprehensive (Broad) 20000007 Drug Related Hepatic Disorders - Severe Events Only (Narrow)

- a. An AE will be considered concurrent with cytopenia event if the onset date is no more than 7 days prior to the onset of the cytopenia and no more than 7 days after the end of the cytopenia event.
- b. The Drug Related Hepatic Disorders – Comprehensive SMQ (20000006) includes all PTs in the Drug Related Hepatic Disorders - Severe Events Only SMQ (20000007). Summaries will be provided for each SMQ.

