Clinical studies conducted to date have assessed safety, pharmacokinetics, and initial efficacy of navitoclax as a single agent and as combination therapy in subjects with hematological malignancies and subjects with solid tumors. The monotherapy recommended Phase 2 dose (RPTD) has been determined as 250 mg in chronic lymphocytic leukemia (CLL) (with a 100 mg lead-in period prior to Cycle 1) and 325 mg under the continuous dosing schedule in small cell lung cancer and other lymphoid malignancies (excluding CLL; with a 150 mg lead-in period prior to Cycle 1), although the starting dose was reduced to 250 mg in lymphoid malignancies as this was found to be more tolerable.⁵⁻⁸

Preclinical data suggest that navitoclax may overcome JAK2 resistance, resensitizing cells to JAK2 inhibition from ruxolitinib, and therefore may provide disease-modifying therapy in subjects with primary myelofibrosis (PMF) and secondary myelofibrosis (SMF).⁶ The combination of navitoclax and ruxolitinib in subjects with MF (Study M16-109) has demonstrated efficacy in subjects with persistent splenomegaly while receiving treatment with ruxolitinib for at least 12 weeks (AbbVie data on file). The median duration of prior ruxolitinib exposure before initiating navitoclax on Study M16-109 was 21 months (range 4 to 71 months). After 24 weeks of treatment with navitoclax and ruxolitinib, 30% of subjects achieved spleen volume reduction ≥ 35% (SVR₃₅). Additionally, spleen responses seem to deepen beyond 24 weeks of treatment, and the best overall SVR₃₅ was further improved to 43%. Symptom improvements were reported in 65% of subjects with 35% of subjects achieving ≥ 50%

reduction from baseline in total symptom score at Week 24. Additionally, reductions in bone marrow fibrosis of ≥ 1 grade were observed in 27% of subjects, suggesting this drug combination may be disease modifying. The safety profile was acceptable with the most common Grade ≥ 3 treatment-emergent AEs reported as thrombocytopenia and anemia. There were no serious adverse events of bleeding. There was 1 treatment-emergent death due to pneumonia that was assessed by the investigator as having no reasonable possibility of relationship to navitoclax.

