2.2 Benefits and Risks to Subjects

Ruxolitinib (a dual Janus kinase 1 [JAK1] and JAK2 inhibitor) and fedratinib (dual JAK2 and FMS-like tyrosine kinase 3 [FLT3] inhibitor) are approved by numerous regulatory bodies worldwide for the treatment of myelofibrosis. While the approval of these JAK2 inhibitors has changed the treatment landscape for patients with myelofibrosis, their therapeutic remit is aimed at improving symptoms and quality of life. The only treatment modality capable of curing MF is allogeneic HSCT. The applicability of HSCT is limited by the inherent risks in this population, with their attendant comorbidities.

Preclinical data suggest that the combination of navitoclax with ruxolitinib may provide disease-modifying therapy for patients with PMF or SMF. Clinical studies (single-agent and combination therapy) have assessed the safety, pharmacokinetics and initial efficacy in subjects with hematologic malignancies or in subject with solid tumors.

Risks observed in nonclinical and/or clinical studies associated with navitoclax administration are thrombocytopenia, lymphopenia, and neutropenia. Thrombocytopenia has been the primary

dose-limiting toxicity. Navitoclax accelerates apoptosis, rather than lysis, of circulating mature platelets whether endogenous or transfused. This mechanism of action differs from the thrombocytopenia caused by conventional chemotherapy (i.e., toxicity to platelets progenitors in the bone marrow) and should, therefore, be managed. Actions are in place in study protocols to mitigate these risks and, when medically indicated, to treat these effects; these include appropriate patient selection, careful monitoring, and treatment management guidelines.

The most common treatment emergent hematological adverse reactions of any grade with an incidence > 10% reported with navitoclax in combination with ruxolitinib (Study M16-109; Cohort 3) in patients with MF who have not previously received ruxolitinib are thrombocytopenia, neutropenia, and anemia. The most common treatment emergent nonhematological adverse reactions of any grade with an incidence \geq 10% are nausea and diarrhea.

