Subjects who do not receive any study drug will be treated as non-responders. Subjects who are baseline transfusion independent and whose baseline hemoglobin is ≥ 10 g/dL will not be included in the analysis since these subjects are not applicable to the evaluation of anemia response.

Anemia response rate is defined as the proportion of subjects who achieve anemia response and will be analyzed using the statistical method described for binary variables in Section 8.1. The main analysis of anemia response will include both TD and TI subjects, with separate summaries provided for TD and TI subjects.

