9.2.3 Treatment-Emergent Adverse Events by SOC and/or PT

Treatment-emergent adverse event summaries will be presented by SOC and PT. Specific adverse events will be counted once for each subject for calculating percentages, unless stated otherwise. In addition, if the same adverse event occurs multiple times within a subject, the highest severity and level of relationship to investigational product will be reported.

In addition, treatment-emergent adverse events will be summarized by PT and sorted by decreasing frequency for the navitoclax + ruxolitinib arm, and summarized by SOC, PT and maximum NCI grade.

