9.2.5 Safety Topics of Interest

The safety topics of interest identified using standard MedDRA queries (SMQs) and custom searches are provided in [Appendix B](#).

The incidence of each safety topic of interest will be summarized by SOC and PT. The AEs overview described in Section 9.2.2 and a listing of subject data will be provided for each search.

In addition, for each search, the risk difference for the overall incidence and the corresponding 95% confidence interval (CI) will be computed and displayed in a forest plot and summary table. The risk difference will be defined as the incidence proportion of the navitoclax + ruxolitinib treatment arm minus the incidence proportion of the placebo + ruxolitinib treatment arm. The normal approximation to the binomial distribution will be used to compute the 95% CI.

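### Anemia is not a safety topic in SAP Appendix B, so its adverse events get no grouped-term incidence and no risk difference with a confidence interval

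*SAP*

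**What the plan says.** **Anemia as a known harm.** Protocol 2.1, on Study M16-109 subjects already exposed to ruxolitinib, states: "The safety profile was acceptable with the most common Grade ≥ 3 treatment-emergent AEs reported as thrombocytopenia and anemia". Protocol 2.2, on the combination in Cohort 3 of that study, says that the most common hematological reactions above 10% "in patients with MF who have not previously received ruxolitinib are thrombocytopenia, neutropenia, and anemia". Protocol 2.2 also names anemia among the hematological reactions above 20% with ruxolitinib alone. Protocol 4.2 names it, with thrombocytopenia, as a main reason for ruxolitinib dose reduction.

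**Safety topics.** SAP Appendix B is introduced by "Safety topics of interest will be identified using the following search criteria". The topics are thrombocytopenia, neutropenia, hemorrhagic events, serious hemorrhage concurrent with Grade 3 or 4 thrombocytopenia, serious infections, serious infections concurrent with Grade 3 or 4 neutropenia, and drug-induced liver injury. The thrombocytopenia and neutropenia searches each join diagnosis terms with a count-decreased term. For every topic SAP 9.2.5 provides the adverse event overview and a subject listing, and "for each search, the risk difference for the overall incidence and the corresponding 95% confidence interval (CI) will be computed", shown in a table and a forest plot. SAP 9.5 repeats the topic overviews by subgroup.

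**Other adverse event tables.** Under SAP 9.2.3, events are also "summarized by SOC, PT and maximum NCI grade". Preferred terms are not grouped there.

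**Anemia as a benefit.** Anemia response ranks third among the key secondary endpoints in Protocol 7.6. It is step 4 of SAP Table 1, at two-sided 0.05. SAP 8.4.1.4 adds: "Subjects who are baseline transfusion independent and whose baseline hemoglobin is ≥ 10 g/dL will not be included in the analysis".

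**The concern.** The sponsor treats two of the three named hematological reactions as topics and leaves out the third, without giving a reason. The consequence is an imbalance in how anemia is reported. Improvement gets a stratified test within the alpha-controlled sequence. Worsening gets by-arm counts with no planned contrast.

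The ranked endpoint cannot fill the gap. It counts improvement only, and it leaves out transfusion-independent subjects who start at 10 g/dL or above, so new anemia in them cannot appear there.

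At stake is a prespecified answer to a natural question for a placebo-controlled add-on trial: does adding navitoclax to ruxolitinib change the frequency, severity or dosing consequences of anemia? If the terms are pooled and the difference computed only after unblinding, the choice of terms is open to challenge.

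**Working it through.** The plan states no figure on this point, so there is none to reproduce. The check is a comparison of planned outputs, followed by two illustrations.

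**Step 1. Planned outputs side by side**

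| Output | Thrombocytopenia | Neutropenia | Anemia |
|---|---|---|---|
| Counts by SOC, preferred term, maximum grade (SAP 9.2.3) | yes | yes | yes |
| CTCAE laboratory shift tables (SAP 9.3) | yes | yes | yes, hemoglobin |
| Boxplots and tables by visit (SAP 9.3) | yes | yes | yes, hemoglobin |
| Red cell transfusion summaries (SAP 8.5.2) | – | – | yes |
| Grouped-term search (SAP Appendix B) | yes | yes | no |
| Topic overview of grade, seriousness and effect on dosing (SAP 9.2.5 with 9.2.2) | yes | yes | no |
| Risk difference, 95% CI, forest plot (SAP 9.2.5) | yes | yes | no |
| Topic overview by subgroup (SAP 9.5) | yes | yes | no |

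Platelets and neutrophils have the same laboratory tables as hemoglobin and are topics as well. Having laboratory tables is therefore not, by the plan's own practice, a reason to leave anemia out.

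**Step 2. What separate preferred-term rows can show**

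Let *a* subjects in an arm of *n* have the diagnosis term and *b* the laboratory term. The number with either lies between max(*a*, *b*) and *a* + *b*, so the unresolved range is min(*a*, *b*)/*n* when *a* + *b* ≤ *n*. With 230 subjects randomized 1:1, *n* = 230/2 = 115.

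The counts below are purely hypothetical. The documents give no anemia counts and do not name a hemoglobin-decrease term; that such a term would be used is assumed by analogy with the platelet and neutrophil rows.

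- *a* = 60, *b* = 20: 60/115 = 52.2% to 80/115 = 69.6%, a range of 20/115 = 17.4 points.
- *a* = 60, *b* = 2: 60/115 = 52.2% to 62/115 = 53.9%, a range of 2/115 = 1.7 points.

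The ambiguity may thus be large or negligible, depending on how sites report. It shrinks toward zero if few events carry the laboratory term.

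**Step 3. Precision of the missing estimate**

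SAP 9.2.5 uses the normal approximation, so the 95% half-width is 1.96 × √[p₁(1 − p₁)/115 + p₂(1 − p₂)/115]. The incidences are assumed.

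| p₁ / p₂ | Half-width (points) |
|---|---|
| 20% / 20% | 10.3 |
| 30% / 30% | 11.8 |
| 40% / 40% | 12.7 |
| 50% / 50% | 12.9 |
| 60% / 40% | 12.7 |

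For the first row: 1.96 × √(2 × 0.20 × 0.80/115) = 1.96 × 0.0528 = 0.103. In the last row a true difference of 20 points would exceed the half-width.

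**The case against.** **Worsening anemia is already reported by arm.** This stands. A reader might infer that the plan gives no pooled incidence of worsening at all, and the documents do not support that. The SAP 9.3 shift tables count subjects whose grade worsens and subjects who reach Grade 3 or 4, whatever adverse event term was used. They take the maximum post-baseline grade and include local laboratory data, so a low value recorded before a transfusion still counts. SAP 8.5.2 reports transfusion rate, number and amount.

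Two limits remain. None of these is stated as a between-arm estimate of worsening; at most, the SAP 8.1 default for binary variables could be read to cover transfusion independence, which does not measure worsening. And a laboratory shift is not an adverse event: under Protocol 6.1 an abnormal value becomes one only in certain circumstances. The shift tables do not show seriousness or effect on dosing.

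**The topic list has a logic.** Protocol 2.2 gives the risks associated with navitoclax as thrombocytopenia, lymphopenia and neutropenia. Protocol Table 1 adjusts doses for platelets and neutrophils, and both feed the concurrent-event searches. This makes the omission a selection judgment rather than a contradiction. But that list does not by itself define the topics: lymphopenia is on it and is not a topic, and liver injury is a topic without being on it.

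**Navitoclax may add little anemia.** A reader might infer that both drugs are expected to cause anemia, or that anemia would be among the largest differences between arms. Neither is supported. The documents attribute anemia to the combination and to ruxolitinib, both arms receive ruxolitinib, the Grade ≥ 3 statement comes from ruxolitinib-exposed subjects, and no incidence by arm is given. Not knowing the difference is a reason to estimate it.

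**The exclusion in the anemia response analysis is natural.** Agreed: a response requires anemia at baseline. The exclusion is no flaw in that endpoint; it only means that the endpoint cannot stand in for a harm analysis.

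**Conclusion.** The point holds in a limited form. The protocol names anemia as a leading reaction to the combination and to ruxolitinib, yet it is the only one of the three hematological reactions named for ruxolitinib-naive subjects without a safety topic. As a result it has no grouped-term adverse event incidence, no topic overview, and no risk difference with confidence interval, while its improvement is formally tested. Worsening is visible by arm, but descriptively.

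This is a gap in safety presentation. It changes no efficacy inference, no alpha and no sample size. Its numerical effect cannot be derived from the documents: the 52% to 70% example is hypothetical, and the 10 to 13 point half-widths rest on assumed incidences and 115 subjects per arm. The change is still worth making, because it applies the sponsor's own method to a named harm at almost no cost.

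**What to change.** Add an Anemia row to SAP Appendix B that pools prespecified anemia and hemoglobin-decrease preferred terms, built like the thrombocytopenia and neutropenia rows. The exact terms should be fixed from the coding dictionary before treatment codes are released for the primary analysis. SAP 9.2.5 then supplies the overview, listing, risk difference with 95% CI and forest plot entry, and SAP 9.5 the subgroup overviews.

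Report the result beside the hemoglobin shift tables and the SAP 8.5.2 transfusion summaries, so that events, laboratory grades and transfusion use can be read together.

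The cost is one table row and one more pass of existing programs. No new data, alpha or change to clinical management is involved.
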